8. STUDY PROCEDURES

After signing consent, all subjects will undergo randomization and study related procedures, as well as standard of care procedures, per Table 1 and as indicated below.

All subjects will either have a functional CIED already implanted prior to AF ablation, at time of AF ablation or within 24 hours following AF ablation as standard of care.

All subjects enrolled in the study will remain on SOC medications and participation in the study will not require discontinuation of any SOC medications.

Intervention Management Arm (Dapagliflozin)

A block randomization method will be use to randomize subjects to treatment with dapagliflozin 10 mg once daily versus placebo. Subjects will take 1 blinded tablet of study drug (dapagliflozin) dosed once daily, per the randomization scheme, for a 6-12 month duration depending on date of randomization. All active and placebo tablets will be identical in appearance (same size, shape and color). Subjects will be encouraged to start study drug within 2 weeks of the date of randomization. Study subjects will be instructed to ingest all tablets whole and not to open them. Each subject will be dispensed 35 blinded doses per month, during each month of participation in the trial. Quarterly pill counts will be performed to track compliance. All drug dispensing (dapagliflozin and matching placebo) will be managed by the Investigational Drug Services (IDS) in the Department of Pharmacy at the University of Rochester Medical Center. The unit manages drug dispensing for numerous clinical trials and

has vast experience in this field. Any study related side effects will be reported to the independent Data and Safety Monitoring Board (DSMB) for review (details below). The cost of study drug will be covered by the study.

Patients with diabetes who are started on dapagliflozin will continue to undergo standard of care glucose monitoring as directed by the primary treating physician. The initiation of dapagliflozin does not require any incremental testing/monitoring beyond what is performed as standard of care.

IDS is in full compliance with federal, state, Joint Commission on Accreditation of Healthcare Organizations (JCAHO), and American Society of Health-System Pharmacists (ASHP) requirements regarding control of investigational drugs. Investigational drugs will be stored in both the IDS and the Department of Pharmacy to ensure appropriate access, security, stability, and compliance with FDA guidelines. Drug order, receipt, and return forms will be maintained for all medications used in the clinical trial. Drug accountability records will be maintained for all study drug received, stored, dispensed and destroyed by the IDS. Study drug supplies will be inventoried on a regular basis for quality assurance purposes. IDS will maintain records after study completion according to FDA requirements, or as specified per protocol. JCAHO requires that anyone administering an investigational drug have a working knowledge of the drug, such as its purpose, side effects, precautions, and procedures for administration. All IDS personnel involved in the trial will receive the necessary training to ensure full compliance with good clinical practice guidelines.

Control Arm (Placebo)

Subjects will take 1 blinded tablet of placebo drug dosed once daily, per the randomization scheme, for a minimum duration of 6 months and maximum duration of 12 months.

Procedures for Both Groups – Regardless of Randomization:

Post-randomization, follow-up of subjects in each arm will include SOC visits at 3, 6, 9 and 12 months. When feasible these will be virtual (TeleHome) visits in order to minimize study related burden on enrolled subjects. Study related adverse events and protocol deviations will be recorded during each of these SOC visits. CIED interrogation data will be obtained either via remote CIED downloads or during in-office visits. The interrogation data will be acquired in a standardized PDF format. The interrogation report will de-identified. All protected health information will be removed and subject ID will be entered for tracking. The de-identified PDF file will be uploaded to the study web-based data management system in a HIPAA compliant manner. CIED interrogation reports will be reviewed by an independent Events Adjudication Committee, blinded to treatment assignment. The final SOC visit will take place in-office, during which time all study related procedures and assessments will be completed.

Standard of Care Procedures

• In-office or TeleHome follow up visits as scheduled will occur at 3, 6, 9 and 12 months. These visits will include a medical assessment, drug accountability/compliance, device interrogation, and subjects will be questioned about clinical and medical (adverse) events.

- 12 lead ECGs if performed as SOC at Baseline, 3 months, 6 months, 9 months and 12 months.
- Remote interrogation data from CIED will be collected.
- Echocardiographic data if performed as SOC.
- Blood sugar monitoring in diabetics per SOC.

Research Activities:

- Chart reviews will be performed by the study team at each time point and include data about clinical history, medications, ablation procedure, device implantation, and follow-up data will be collected from the medical record.
- Assessment of healthcare utilization (comprising the total of unplanned in-office visits, hospitalizations, repeat ablations, or death).
- AFEQT questionnaires will be completed by the subject at baseline and the final follow-up visit. The questionnaire should take the subject approximately ten minutes to complete. We will utilize an instrument specifically designed for patients with AF, the Atrial Fibrillation Effect on QualiTy-of-Life (AFEQT), a questionnaire focusing on symptoms, daily activities, treatment concerns and treatment satisfaction.

Method of Assigning Subjects to Treatment

Subjects will be randomized 1:1 to Dapagliflozin versus placebo. Randomization will occur electronically using the electronic data collection system, TrialMaster that is available 24/7 to all study personnel.

Follow-up 3, 6, 9, 12 months (See Table 1)

Following enrollment and randomization all subjects will have SOC follow-up in-office or TeleHome visits at 3, 6, 9 and 12 months. TeleHome videoconferencing visits may be replaced with in-office visits as needed.

All subjects will be followed for a time-period of a minimum of 6 months and maximum of 12 months.

The following study related data will be collected during SOC visits after ablation.

- 3 Months ± 1 calendar months from study drug initiation date
 - Review of medical history including adverse events, hospitalization, unplanned office visits, and emergency room visits
 - o Study drug accountability and compliance
 - Current cardiac medication
 - o Blood sugar values in diabetic patients
 - Assessment of symptoms
 - 12-Lead ECG (if done per standard of care)
 - CIED Interrogation
- 6 Months ± 1 calendar months from study drug initiation date
 - Review of medical history including adverse events, hospitalization, unplanned office visits, and emergency room visits

- Study drug accountability and compliance
- Current cardiac medication
- Blood sugar values in diabetic patients
- Assessment of symptoms
- 12-Lead ECG (if done per standard of care)
- CIED Interrogation
- AFEQT Questionnaire (if final follow-up visit)
- 9 Months ± 1 calendar months from study drug initiation date
 - Review of medical history including adverse events, hospitalization, unplanned office visits, and emergency room visits
 - Study drug accountability and compliance
 - Current cardiac medication
 - Blood sugar values in diabetic patients
 - Assessment of symptoms
 - 12-Lead ECG (if done per standard of care)
 - CIED Interrogation
 - AFEQT Questionnaire (if final follow-up visit)
- 12 Months ± 1 calendar months from study drug initiation date
 - Review of medical history including adverse events, hospitalization, unplanned office visits, and emergency room visits
 - Study drug accountability and compliance
 - o Current cardiac medication
 - Blood sugar values in diabetic patients
 - o Assessment of symptoms, NYHA functional class
 - 12-Lead ECG and Echocardiogram data (if done per standard of care)
 - CIED Interrogation
 - AFEQT Questionnaire

Communication at Randomization and the Conclusion of the Final Follow-up Visit

In order to maintain oversight and continued clinical management, the site PI will communicate by letter with the subject's treating physician that the subject is randomized and participating in the study. Also, at the conclusion of the final treatment visit, if the patient tolerated the study drug (Dapagliflozin or placebo), the site PI will communicate by letter with the subject's treating physician that it is recommended that the subject be treated with an SGLT2 inhibitor per FDA-approved indication.

Reportable	Screen/	Baseline	In-Office or	In-Office or	In-Office or	In-Office or
Data Items	Consent/		TeleHome	TeleHome Visit	TeleHome Visit	TeleHome Visit
	Randomization		Visit	6 months	9 months	12 months
			3 months			
Timeframe	Confirm	Following	3 months $(+/-1)$	6 months $(+/-1)$	9 months $(+/-1)$	12 months (+/-
	eligibility,	randomization	calendar month)	calendar month)	calendar month)	1 calendar
	consent,		after date of	after date of	after date of	month) after
	randomize		study drug initiation	study drug initiation	study drug initiation	date of study drug initiation
Inclusion/Exclusion	√		Initiation	Initiation	Initiation	drug initiation
Informed Consent	ν					
Demographics		\checkmark				
Medical/Cardiac						
History						
Limited Physical						
Exam/NYHA						
AF Ablation*		\checkmark				
CIED Device*		\checkmark				
AFEQT				$\sqrt{***}$	$\sqrt{***}$	\checkmark
Questionnaire						
CV and Diabetes		\checkmark	\checkmark	\checkmark		
Medication Log*			1	1		1
ECG*			√	√		۸
LVEF		\checkmark				\checkmark
(Echocardiogram)*				1		1
HbA1c** (per SOC)		√		√		√
Study Drug		\checkmark	\checkmark		\checkmark	
Initiation/						
Accountability			1	1	1	1
CIED Interrogation				\checkmark		\checkmark
and Activity Data* Follow-up		√			√	
Follow-up Contact/Cardiac		N N	\checkmark	N N	-N	\checkmark
Events/Procedures/						
Glucose**						
Adverse Events, HF		\checkmark		\checkmark		
hospitalization,						
Unplanned						
hospitalization,						
office, remote or ER						
visit, death		1	1		1	1
Protocol Deviations		\bigvee	√ . 1 ****10 ° . 1	√ \		

 Table 1: Schedule of Activities

* Standard of care procedures ** Diabetic subjects only ***If final follow-up visit

Plans for return of research results:

Research results will not be provided directly to subjects, but will be presented in national conferences and published in peer-reviewed papers after study completion. If requested by subjects we will send the published research results to subjects. Subjects will be notified if anything of medical importance is found.

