4.1. SUBJECT POPULATION

The study population will include subjects undergoing catheter ablation of AF with an implanted CIED or indication for CIED that can be implanted prior to randomization per Figure 3.

Consented eligible subjects will be randomized in a 1:1 ratio to either intervention (dapagliflozin 10 mg once daily) or control (placebo); About 13 or 12 subjects enrolled to each group for a total of 25 subjects across all enrolling sites. After enrollment (consent), QoL assessment will be obtained using the AFEQT questionnaire. The subjects will then undergo the index catheter ablation of atrial fibrillation. If CIED does not exist prior to consent then CIED implant will occur prior to, during or within 24 hours of the ablation procedure. Following catheter ablation and successful CIED

implant, the subject will be randomized, baseline data collected and the subject will be followed over a minimum duration of 6 months and up to 12 months duration depending on date of randomization. Subsequent study visits visit will be virtual (through phone contact and/or videoconferencing) in which: a) remote de-identified CIED interrogations will be transmitted to the CDC by the site research coordinator; b) follow-up data on subject status, study drug accountability/compliance, and healthcare utilization/adverse events will be obtained. QoL testing will be repeated at the 12-month follow-up visit. We believe that the virtual approach to study visits and data collection will contribute to significantly higher acceptance and enrollment than in previous studies.

Follow-up visits will be done at 3, 6, 9 and 12 months following randomization.

The study duration is 3 years including a planned study startup period of 6 months, an enrollment period of 18 months, a follow-up period of 6 months, and 6 months for closeout and analysis.

4.2. **STUDY INTERVENTIONS**

Please see section 8 entitled study procedures that includes further study interventions.

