17. DATA ANALYSIS PLAN

Descriptive statistics will be used to evaluate the rates related to the primary endpoint and health care utilization and HF hospitalization secondary endpoints for each group in the study population. Further, mean quality of life AFEQT scores will also be reported. General linear models will be used to identify factors associated with the risk of both AF burden and recurrent endpoints during follow-up.

For the primary endpoint of AF burden, defined as percentage of time spent in AF (i.e. **amount of time spent in AF divided by the total amount of time a patient was monitored**), the student's t-test will be used to statistically compare the placebo group vs. the active treatment group. This approach is subject to an examination of the distribution of the percent time in AF.

Currently, patients with persistent AF account for >60% of the AF ablation volume in each of the enrolling sites and therefore we anticipate a higher burden of AF than what has been reported in patients with paroxysmal AF, including CAPTAF (in which patients with paroxysmal AF)

comprised 70% of the study population).⁴²

Our preliminary data on 125 patients implanted with an ICM at URMC of whom 65% had persistent AF, show an overall AF burden of 25%. Other published studies have shown a higher burden of AF in persistent AF populations.⁴³ In the present study, enrollment will use a stratified proportionate allocation in a 2:1 ratio by type of AF (persistent vs. paroxysmal, respectively) to ensure a sufficient proportion of subjects with persistent AF.

Sample size

Our re-estimated power calculations are based on the following parameters:

- 1. 25 subjects randomized
- 2. Minimum follow-up of 6 months, average follow-up of 9 months.
- 3. Our preliminary interrogations suggest that we may have underestimated AF burden (possibly due to the higher risk characteristics of enrolled patients with heart failure, diabetes, and renal dysfunction). The revised AF burden estimate takes a conservative measure of at least 40%.

The Table below provides power calculations for a treatment effect in the range of 40% to 50%.

			SD		sample		total
	Average AF	Average AF					
	burden:	burden:					
Reduce	placebo	Intervention	deviation	power	size	dropout	sample
50%	40%	20.0%	15%	85%	23	10%	25
45%	40%	22.0%	15%	76%	23	10%	25
4370	4070	22.070	1370	/0/0	25	1070	23
43%	40%	22.8%	15%	73%	23	10%	25
40%	40%	24.0%	15%	66%	23	10%	25

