Based on our preliminary interrogation data above, the primary outcome of AF burden over an average follow-up of 9 months is assumed to be 40% in the placebo group and 20-24% in the intervention (dapagliflozin) group, with a standard deviation of 15% (a conservative estimate which allows for 10% drop-out). With a sample of 25 subjects randomized, a reduction from 40% to 20%-22% would provide 85%-76% power, respectively. Other possible scenarios are provided in the Table above.

We therefore, believe that the study may be the first to provide pilot prospective data on the possible antiarrhythmic properties of dapagliflozin following AF ablation.

The study power should not be affected by the association of diabetic status and cardiovascular medications with the study drug, Dapagliflozin, or AF burden, the primary outcome of the study. Further, prior publications have not shown differential effects of this drug within diabetic status or medication subgroups. Also, because the study drug and placebo groups will be randomly

assigned the distribution of diabetic patients and use of cardiovascular medications should be similar in the two. We will perform a sensitivity analysis where we adjust for diabetics and heart failure both parametrically and non-parametrically. Finally, the study was not designed to be powered to look for affects in subgroups of the study population, only in the overall enrolled study group.

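### No stratification of randomization by AF type is stated; if there is none, 25 subjects carry a 20-23% chance of a 25-point or larger arm difference in persistent AF

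*Combined protocol and SAP*

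**What the plan says.** Treatment assignment is described in Sections 4, 4.1 and 8. Section 8 (Intervention Management Arm) states: "A block randomization method will be use to randomize subjects to treatment with dapagliflozin 10 mg once daily versus placebo". Under Method of Assigning Subjects to Treatment it adds: "Subjects will be randomized 1:1 to Dapagliflozin versus placebo", carried out electronically in TrialMaster. Section 4.1 gives the size: "About 13 or 12 subjects enrolled to each group for a total of 25 subjects across all enrolling sites". None of these places gives a block size or a stratification factor.

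AF type is used as a stratifier only in Section 17: "enrollment will use a stratified proportionate allocation in a 2:1 ratio by type of AF", persistent to paroxysmal. The stated aim is "to ensure a sufficient proportion of subjects with persistent AF". The same section gives the reason AF type matters: "Other published studies have shown a higher burden of AF in persistent AF populations".

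The primary comparison in Section 17 is an unadjusted Student's t-test, subject to a look at the distribution. The sensitivity analysis adjusts for diabetes and heart failure; AF type is not listed. For other baseline factors the plan relies on chance: because groups are randomly "assigned the distribution of diabetic patients and use of cardiovascular medications should be similar in the two" groups.

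**The concern.** Blocking without strata equalizes arm sizes. It does nothing to equalize the number of persistent-AF subjects per arm, and neither does an enrollment quota. A 2:1 ratio cannot describe a 1:1 treatment assignment, so the plainer reading of Section 17 is that it governs entry only.

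AF type is the one factor the plan uses to control enrollment, and the plan expects it to drive the primary endpoint. (Section 17 also suggests that heart failure, diabetes and renal dysfunction raise burden, so AF type is not the only prognostic factor.) Yet the documents name AF type neither as a randomization stratum nor as a covariate in the treatment comparison. With 12 or 13 subjects per arm, randomization alone leaves a material chance of uneven arms. A reader could then attribute a positive or a null result to the AF-type mix.

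**Working it through.** **The plan's own power figures.** Inputs from Section 17: 23 analysed, SD 15, placebo burden 40%, intervention 20 to 24%. Alpha is not stated; two-sided 0.05 is assumed. The noncentral-t power for 11 per arm is 84.5, 76.3, 72.5 and 66.3% for differences of 20, 18, 17.2 and 16 points. The table gives 85, 76, 73 and 66%, so it is reproduced. With 23 analysed as 12 and 11, the standard error of the difference is 15 × √(1/12 + 1/11) = 6.3 points.

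**Number with persistent AF.** 25 × 2/3 = 16.7, so 16 or 17.

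**Chance of imbalance without stratification.** With K persistent among 25 and arms of 13 and 12, the number x in the larger arm is hypergeometric:

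P(x) = C(K, x) × C(25 − K, 13 − x) / C(25, 13), with C(25, 13) = 5,200,300.

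The arm difference is x/13 − (K − x)/12. For K = 17:

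| Persistent, 13-arm / 12-arm | Difference (points) | Probability |
|---|---|---|
| 5 / 12 | −61.5 | 0.0012 |
| 6 / 11 | −45.5 | 0.0190 |
| 7 / 10 | −29.5 | 0.1047 |
| 8 / 9 | −13.5 | 0.2618 |
| 9 / 8 | 2.6 | 0.3272 |
| 10 / 7 | 18.6 | 0.2094 |
| 11 / 6 | 34.6 | 0.0666 |
| 12 / 5 | 50.6 | 0.0095 |
| 13 / 4 | 66.7 | 0.0005 |

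The rows at 25 points or more sum to 20.2%. For K = 16 the sum is 22.6%, and the smallest qualifying difference is 26.9 points. For either K the chance is 41% at 15 points or more and 9.7% at 30 or more.

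**Sensitivity.**
- Simulated central lists with blocks of 2, 4 or 6: 19.6 to 23.1%.
- Separate lists for 7 sites, assumed to recruit equally: 16 to 22%.
- AF type random at 2/3, with no quota: 20.2%.
- 23 analysed as 12 and 11, with 15 or 16 persistent: 19.3%.

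**Size of the consequence.** The shift in the observed difference is imbalance × burden gap between AF types. The gap is an assumption, but the plan's SD bounds it. If 15 is the SD over the 2:1 mix, then 15² = (within-type SD)² + (2/3)(1/3) × gap², so the gap cannot exceed √(225 / 0.222) = 31.8 points. For gaps of 10 to 30 points, a 25-point imbalance shifts the difference by 0.25 × 10 = 2.5 to 0.25 × 30 = 7.5 points. At 29.5 points, the first attainable value past 25 with 17 persistent, the shift is 2.9 to 8.8. The planned effect is 40 − 24 = 16 to 40 − 20 = 20 points.

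**Effect of stratifying all 25 by AF type.** With a central list and blocks of 2, 4 or 6, an imbalance of 25 points or more occurred in 0 of 20,000 simulated trials per setting. Crossing AF type with 7 sites leaves 1 to 14%, because most blocks stay incomplete.

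For a 20-point gap, the within-type SD is √(225 − 88.9) = 11.7. The SD of the treatment estimate then falls from 15 × √(1/13 + 1/12) = 6.0 to 11.7 × 0.400 = 4.7. An unadjusted t-test would still use a standard error near 6.0. Its critical difference is 2.07 × 6.0 = 12.4 points, or about 2.7 true SDs, so its type I error drops to about 1%.

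**The case against.** Five counterarguments deserve weight.

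1. **The documents are silent, not explicit.** A reader might infer that randomization is definitely unstratified. The text does not say so, and the words used in Section 17 could loosely cover a stratified randomization list. This stands, so the 20-23% is conditional on there being no such stratum.

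2. **Chance imbalance is not bias.** A reader might conclude that the t-test is invalid. It is not: its standard error already allows for random imbalance, and simple blocking is a legitimate method, particularly for what Section 17 calls pilot data. This stands. The loss is in precision and credibility.

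3. **Adjustment recovers nearly all the precision.** For 17/8 and 13/12, r² = imbalance² × (13 × 12)/(17 × 8). At 25 points r² = 0.072 and the standard error rises by a factor of 1/√(1 − 0.072) = 1.04; at 29.5 points the factor is 1.05. It would be wrong to say that later adjustment cannot help. But no AF-type adjustment of the treatment comparison is planned. The general linear models in Section 17 are for finding factors associated with burden, and they name none.

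4. **Stratifying alone would not improve the reported result.** As shown above, it makes the unadjusted t-test conservative. This stands, and the fix therefore has two parts.

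5. **Enrollment appears to have begun.** Section 17 speaks of a re-estimated calculation and of enrolled patients. Stratifying only the remainder (17/8, blocks of 4) leaves a chance of a 25-point imbalance of 8% if 12 are already randomized, 12% if 16, and 17% if 20. The documents do not give the number.

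**Conclusion.** The point holds as a conditional one. No stratification of randomization by AF type is stated, and the 2:1 rule does not balance the arms. If AF type is not a stratum, roughly one trial in five of this size would differ by 25 points or more in the share with persistent AF. That figure rests on 16 or 17 persistent of 25 and arms of 13 and 12, and a central list's block size hardly moves it. The resulting shift of 2.5 to 7.5 points rests on an assumed AF-type gap of 10 to 30 points. At the upper end it exceeds one standard error and is over a third of the planned effect; at the lower end it is minor. Larger gaps, above about 32 points, contradict the plan's own SD. An inexpensive change is worth making, but the concern does not invalidate the design.

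**What to change.** State in Section 8 the block scheme and whether AF type is a randomization stratum. If it already is, that sentence settles the allocation question. If it is not:

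- For all subjects still to be randomized, set TrialMaster to use permuted blocks within AF type (persistent, paroxysmal). Do not cross this with the 7 sites.
- In Section 17, replace the unadjusted t-test with a linear model containing treatment and AF type as the primary comparison. If the planned look at the distribution rules this out, keep AF type as a stratum in the rank-based alternative. The covariate is needed whether or not stratification is added: it realizes the precision gain, keeps the test from being conservative, and covers subjects already randomized.

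The cost is a system configuration change, a protocol sentence, the matching edit to the analysis plan and one model degree of freedom. AF type must already be known to run the enrollment quota, so no new data are required. The gain from stratifying shrinks with each subject already randomized; the gain from the covariate largely does not.
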